## **PROTOCOL SYNOPSIS**

Title	Study on avatrombopag for the promotion of platelet engraftment after allo-HSCT
---------------------	---------------------------------------------------------------------------------

Version	1.0
Population	Patients with thrombocytopenia after allogenic hematopoietic stem cell transplantation (Allo-HSCT)
Objective	To evaluate the efficacy and safety of avatrombopag in the treatment of thrombocytopenia after Allo-HSCT, and provide evidence-based instruction of avatrombopag in promoting hematopoietic function reconstruction and reducing PLT transfusion for patients with delayed PLT reconstruction after Allo-HSCT in clinical practice
Design	Single, prospective, randomized controlled trial
Subject Number	78 participants
Eligibility Criteria	
Inclusion criteria
 
Each participant must meet all of the following criteria:
 
 
1. Male or female, aged between 18-60 years;
 
2. PLT has not been reconstructed 14 days after Allo-HSCT (PLT reconstruction was defined as the status of peripheral PLT count <math>> 20 \times 10^9/L</math> for consecutive 7 days without the need for PLT transfusion);
 
3. Expected survival time <math>> 3</math> months;
 
4. ECOG performance status 0-2;
 
5. Agree to receive the treatment of avatrombopag after Allo-HSCT and must sign the informed consent form.
 
 
Exclusion criteria
 
Participant meets any of the following criteria will be excluded from this study:
 
 
1. Pregnant or lactating;
 
2. With severe and uncontrollable infection;
 
3. With graft-versus-host disease (GVHD) with steroid
 

resistance;

4. With thrombotic microangiopathy;
5. With active thromboembolism requiring anticoagulation
6. With detected disease recurrence due to chimerism by flow cytometry;
7. With chronic active hepatitis B and C virus infection;
8. With secondary or multiple transplantation, or multiple organ transplantation;
9. With severe heart disease, lung disease, diabetes and metabolic diseases;
10. HIV positive;
11. With a history of PLT dysfunction or bleeding disorders
12. With the active hepatic venous occlusion disease, or a history of clinically significant hepatic venous occlusion disease (The disease was defined as the abnormal condition of painful hepatomegaly after transplantation with bilirubin  $\geq 6.0$  mg/dL);
13. With progressive solid tumor;
14. With severe bleeding requiring transfusion of more than 2 units of red blood cells, or sudden drop of blood cell volume  $\geq 10\%$  within 7 days prior to screening;
15. With any other clinical trial of investigational product or device within 30 days prior to the baseline visit, except for observational study;
16. With treatment of thrombopoietin receptor agonist (TPO-RA) one month before enrollment;
17. Deemed unsuitable for enrollment by the investigator.

[figure not shown]

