**Outcome Measure**

**Primary outcome measures**

- Percentage of participants whose PLT reaches ≥

	
20*10^9/L without the need for PLT transfusion for consecutive 7 days during core study
 
Secondary outcome measures
 
 
• Percentage of participants whose PLT reaches ≥ 20*10^9/L without the need for PLT transfusion for consecutive 7 days during extended study;
 
• Percentage of participants without PLT response in the standard group but with PLT reconstruction after receiving avatrombopag;
 
• Percentage of participants with PLT ≥ 50*10^9/L without the need of PLT transfusion for consecutive 7 days during the core and extended study;
 
• The time to achieve PLT ≥ 20*10^9/L without the need of PLT transfusion for consecutive 7 days in both group;
 
• Proportion of participants achieving platelet reconstitution after 4 weeks of drug withdrawal;
 
• Volume of PLT transfusion;
 
• Hematopoietic reconstruction condition (absolute neutrophils, hemoglobin)
 
 
PLT reconstruction is defined as the status of PLT ≥ 20*10^9/L without the need of PLT transfusion for consecutive 7 days.

pSafety Measure
	
 
1. Liver and renal functions;
 
2. Occurrence and severity of transplantation-related complications;
 
3. Bleeding risk (WHO bleeding assessment scale);
 
4. Adverse events.
 

Study
	
Screening stage (Day 10~14 after Allo-HSCT)

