
process
	
 
1. Informed consent;
 
2. Subject's demographic information and basic information;
 
3. Medical history, current treatment, concomitant medication;
 
4. Vital signs, physical examination;
 
5. Transplantation mode and preprocessing scheme;
 
6. Blood test: blood routine, blood biochemical (including liver and renal functions), virus infection;
 
7. Pregnancy tests (women of childbearing age);
 
8. Eligibility criteria review.
 
 
Visit 1(Day 15 after Allo-HSCT, Initial treatment)
 
 
1. Blood test: blood routine, blood biochemical (including liver and renal functions);
 
2. Vital signs, physical examination;
 
3. Concomitant medication, including PLT transfusion;
 
4. Adverse events.
 
 
Visit 2-9 (one visit per 1~2 weeks. Visit 2, day 21±2; visit 3, day 28±2; visit 4, day 35±2; visit 5, day 42±2; visit 6, day 49±2; visit 7, day 56±2; visit 8, day 62±2; visit 9, day 70±2 after Allo-HSCT)
 
 
1. Blood test: blood routine, blood biochemical (including liver and renal functions);
 
2. Vital signs, physical examination;
 
3. Concomitant medication, including PLT transfusion;
 
4. Adverse events;
 
 
(Participants who achieved PLT reconstruction during the core and extended study period directly enter the follow up period;
 
Participants who do not respond to the standard

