
Concomitant Treatment
	
 
1. PLT transfusion is allowed according to the bleeding situation: PLT transfusion is given to participant when PLT account < 20*10^9/L, or between 21-60 *10^9/L with active bleeding;
 
2. G-CSF treatment (subcutaneous injection of G-CSF at 5 µg/kg/d from the first day after transplantation until the neutrophils count (ANC) recovered to ≥ 1*10^9/L);
 
3. Cyclosporine A, short courses of mycophenolate mofetil and methotrexate are allowed to use for the prevention of GVHD;
 
4. For medications that have been used before the trial, try to maintain the same dose during the trial;
 
5. Other TPO-RA (such as Eltrombopag and Romiplostim) should be prohibited during the study period;
 
6. Participants are allowed to take concomitant medications that are not specified as prohibited during the study period; Medications used one month prior to screening will be recorded on the case report form. All
 

	
prescription medicines, herbal medicines, nutritional supplements (including vitamins), and over-the-counter medicines should be recorded, as well as any changes in medication taken, including the dose. CYP2C9 or CYP3A4/5 medium or strong inducers may affect the exposure level of avatrombopag in vivo, and medication regimen should be comprehensively assessed by the investigator;
 
7. Observation of adverse events and concomitant medication assessment are conducted for all participants at each visit from the signing of informed consent to the end of the study;
 
8. All concomitant medications should be recorded and described in the corresponding section of the case report form (CRF).

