
Statistical Analysis
	
 
• The sponsor will utilize appropriately qualified individuals to supervise the conduct of the trial to make sure the data collection, entry and management are in accordance with good clinical practice (GCP);
 
• Corresponding database will be established and source data will be input independently;
 
• Data administrator uses Epidata software to compile data entry program and carry out following process. Two data administrators will independently enter and proofread the data in double copies to ensure the accuracy.
 
 
Sample size estimation
 
 
• 78 participants
 
 
Based on the known literature, 35% of patients in the control group and 60% of patient in the trial group were

estimated to achieve the primary endpoint. Under the condition of the number ratio of control to trial group 1:1,  $\alpha=0.05$  (bilateral) and  $1-\beta=0.9$ , the number of participants in the control group and the test group was 79 and 79 respectively, calculated by the pros and cons test method of the clinical controlled study with PASS software. Further taking into account a 20% shedding rate per group, 95 cases per group were actually needed, for a total of 190 cases

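### Entry rule admits patients already in an untransfused platelet run above 20, and neither randomisation nor analysis accounts for it

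*Combined protocol and SAP*

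**What the plan says.** All references are to the protocol synopsis.

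- **Eligibility Criteria.** Inclusion criterion 2 admits a patient if "PLT has not been reconstructed 14 days after Allo-HSCT". Reconstruction is a count above 20 x10^9/L on seven consecutive days with no platelet transfusion. The other inclusion and exclusion criteria set no platelet count and no platelet-transfusion need. The last exclusion is investigator discretion.
- **Objective.** The results are meant to guide use "for patients with delayed PLT reconstruction after Allo-HSCT in clinical practice".
- **Outcome Measure.** The primary outcome is the percentage reaching at least 20 x10^9/L "without the need for PLT transfusion for consecutive 7 days during core study". Neither a low starting count nor a rise from baseline is required. The plan does not say whether all seven days must follow the first dose.
- **Study process.** Screening runs from day 10 to day 14 and is the only stage that lists "Eligibility criteria review". Treatment begins at "Visit 1(Day 15 after Allo-HSCT, Initial treatment". Visit 1 includes a blood count and a record of platelet transfusions. Visit 2 is on day 21±2.
- **Concomitant Treatment.** "PLT transfusion is given to participant when PLT account" is below 20 x10^9/L, so a patient with poor platelet production can read above 20 shortly after a transfusion.
- **Sample size estimation.** "35% of patients in the control group and 60% of patient in the trial group were" expected to reach the primary endpoint.

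**The concern.** The entry criterion is the negation of nearly the same seven-day event that serves as the primary outcome. It removes only patients who have completed the run by day 14; those part-way through remain eligible. Such a patient can become a responder within a week of the first dose by staying where they are, whichever drug they receive.

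If their response depends little on the assigned drug, they raise the percentage in both arms, shorten time to platelet recovery in both arms, and add little to the contrast the trial is designed to detect. They are also a strong prognostic subgroup, identifiable from data taken before the first dose, yet the plan mentions neither stratification nor adjustment for it.

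**Working it through.** **Timing.** A run starting on day s completes its seventh day on day s+6.

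- s = 8: completed on day 14, so the patient is excluded.
- s = 9: completed on day 15.
- s = 14: completed on day 20.
- If all seven days must fall on or after day 15: completed on day 21, the nominal day of Visit 2.

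Runs that began on days 9 to 14 therefore pass criterion 2 and can count as responses on days 15 to 21.

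**The plan's own figure.** Inputs from Sample size estimation: 0.35 v 0.60, two-sided 0.05, power 0.90, 1:1. The unpooled formula gives (1.960 + 1.282)² × (0.35×0.65 + 0.60×0.40) / 0.25² = 78.6, rounded up to 79 per arm, as stated. The synopsis also gives 78 participants in total, which is 39 per arm, so both sizes are carried below.

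**Power formula.** Pooled variance under the null: power = Φ{[d√n − 1.960√(2p̄(1−p̄))] / √[p1(1−p1) + p2(1−p2)]}. For 0.35 v 0.60 this gives 0.890 at 79 per arm and 0.602 at 39.

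**If 35% and 60% describe patients not yet recovering.** Let f be the share already in a run. It is not in the documents; 5%, 10% and 20% are assumptions. If all of them complete the run, control = f + (1−f)×0.35 and trial = f + (1−f)×0.60.

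| f | Control v trial | Difference (points) | Power, 79/arm | Power, 39/arm |
|---|---|---|---|---|
| 5% | 38.3% v 62.0% | 23.8 | 0.854 | 0.556 |
| 10% | 41.5% v 64.0% | 22.5 | 0.815 | 0.512 |
| 20% | 48.0% v 68.0% | 20.0 | 0.725 | 0.431 |

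If only 80% or 90% complete the run, equally in both arms, power at 79 per arm changes by less than 1 point.

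**If 35% and 60% already include them.** Power is as planned: 0.890 at 79 per arm and 0.602 at 39. If they respond alike in both arms, the difference among the remaining patients is 0.25/(1−f), or 26.3, 27.8 and 31.3 points.

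**If the drug also matters in these patients.** Suppose 35% and 60% describe the others, but completion of the run differs by arm (trial v control). Power at 79 per arm for f = 5%, 10%, 20%:

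| Scenario | 5% | 10% | 20% |
|---|---|---|---|
| Kept, 90% v 80% complete | 0.869 | 0.847 | 0.800 |
| Kept, 90% v 70% complete | 0.883 | 0.876 | 0.864 |
| Excluded without replacement | 0.874 | 0.855 | 0.811 |

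At 90% v 80%, excluding them gains only about 0.5 to 1 point. At 90% v 70%, keeping them is better.

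**Gain from adjustment.** Simulation of 40,000 trials per scenario, with 35% and 60% for the other patients, comparing the unadjusted test with a Cochran-Mantel-Haenszel test stratified by entry state:

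- 79 per arm, all complete: 0.849 to 0.872, 0.807 to 0.853, 0.721 to 0.812, a gain of about 2, 5 and 9 points.
- 79 per arm, 90% complete in both arms: adjusted power 0.865, 0.842, 0.778, a gain of about 2, 3 to 4 and 6 points.
- 39 per arm, all complete: 0.573 to 0.583, 0.534 to 0.561, 0.439 to 0.507, a gain of about 1, 3 and 7 points.
- 39 per arm, 90% complete in both arms: a gain of about 0, 2 and 4 points.
- 90% v 70% complete: still a small gain at 79 per arm (about 1 to 3 points), but between −1 and +1 at 39.

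Gains are taken within the simulation because the simulated unadjusted power differs slightly from the formula in small samples.

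**The case against.** The strongest reply is that these patients belong in the trial. Under the plan's own definition, a patient on day 4 of a run has not reconstructed. Doses are tapered only from 50 x10^9/L, and reaching 50 is a secondary outcome, so a patient at 25 is still one the protocol means to treat. A short run can also fail, and sustaining it is something either drug might do. This stands. A reader might infer that these patients lie outside the target population, but the documents do not establish that; excluding them is a choice of population.

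A reader might also infer that the comparison is biased, or that the reported difference is bound to understate the effect. Neither is supported. Randomisation spreads these patients over both arms, so there is no expected imbalance and no inflation of type I error. The difference shrinks only if the benefit in these patients is smaller than in the rest, and the 90% v 70% case shows the loss all but disappearing.

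Finally, a large share may be unlikely. The Population row refers to thrombocytopenia (without a cut-off), investigators may decline a patient, and the dose-increase rule presupposes counts that remain below 20. If the planned rates include these patients, f = 20% would mean that 0.20/0.35 = 57% of expected control responders were already recovering at entry, which is extreme. These points limit the likely size but do not close the gap in the criterion.

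**Conclusion.** The gap in criterion 2 is real: patients part-way through an untransfused run above 20 are eligible and can count as responders in either arm by about day 21. The consequence is conditional. With equal response in both arms, and 35% and 60% describing the others, power at 79 per arm falls from 89% to 85%, 81% or 73% for assumed shares of 5%, 10% or 20%, and at 39 per arm from 60% to 56%, 51% or 43%. If the planned rates already include these patients, nothing is lost against plan. The share is unknown, and so is the drug effect in these patients. What does not depend on either is that entry state is a plausible strong predictor of the primary outcome, is available before treatment, and is not used.

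**What to change.** **Main change.** Stratify randomisation by entry state: below 20 x10^9/L or recently transfused, against 20 or above and untransfused. At the least, adjust the primary comparison for it, for example with a Cochran-Mantel-Haenszel test. Use the Visit 1 blood count and transfusion record, taken before the first dose and, if stratifying, before randomisation. The clinical team should fix the look-back window for a recent transfusion in advance. State in the primary outcome that all seven qualifying days fall on or after day 15.

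**Cost.** No new tests and no patients lost: one randomisation factor and one clause in the outcome. The Statistical analysis method section names no test for comparing two percentages, so the adjusted test displaces nothing. At f = 10% of 78 the smaller stratum has about 8 patients, enough for adjustment but not for a separate result. At 39 per arm, adjustment can cost up to about 1 point of power if the benefit in these patients is similar to that in the rest.

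**Optional alternative.** If the team wants only patients not yet recovering, require a count below 20, or a platelet transfusion within a fixed window, on the last sample before randomisation. This is a choice of target population. It needs an eligibility recheck after screening and leaves fewer eligible patients in a 1.5-year study.

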**Withdrawal criteria**

1. PLT remains less than  $20 \times 10^9/L$  after two weeks' treatment of avatrombopag in a maximum dose of 60

	
mg/d (Solution: receive other treatment after withdrawal from the study);
 
 
2. The participant or his legal guardian requests a withdrawal ;
 
3. c poor compliance(medicine taken less than 80% of the prescribed amount or more than 120% of the prescribed amount);
 
4. With requirement of a medicine that is prohibited in the study;
 
5. With adverse events that discontinues the study;
 
6. With some unexplained serious complications;
 
7. Be pregnant during treatment;
 
8. Deemed unsuitable for further study by the investigator.
 
 
Trial Termination
 
 
1. Sponsor decides to stop the trial for safety reasons;
 
2. Independent ethics committee decides to stop the trial;
 
3. Principal investigator decides to stop the trial.
 

Investigational Product
	
 
• Name: avatrombopag;
 
• Dosage form: tablet;
 
• Specification: 20 mg/tablet.
 

Treatment Design
	
 
• The whole study is divided into two stages, including 4-weeks' core study and 4-weeks' extended study;
 
• During the core study, participants are randomly assigned into the avatrombopag group and the rhTPO treatment group(standard group) with 1:1 ratio. The initial dose of avatrombopag is 20 mg/d. If the patient's PLT count remains less than <math>20 \times 10^9/L</math> after one week, the maximum dose was increased to 40 mg/d.
 
 
Avatrombopag will be taken orally with food. The rhTPO

will be subcutaneously injected with dosage of 300 U/kg/d;

- After the end of the core study, participants in the avatrombopag group who does not meet the withdrawal indication can be enrolled in the extended study and continue the avatrombopag treatment with a maximum dose of 60 mg/d. Participants who does not respond to treatment in the rhTPO group (PLT < 20\*10^9/L ) can also be enrolled in the extended study to receive avatrombopag treatment, by titrating avatrombopag in the dose of 20-60 mg/d according to the participants' condition;
- Patients who achieved PLT reconstruction during the core study and the extended study period are followed up to 4 weeks after investigational product withdrawal, and PLT count is measured for one time during the follow up;
- Adjustment Indication: When PLT ≥ 50\*10^9/L excluding the factor of blood transfusion, the dosage of avatrombopag and rhTPO will be eventually decreased and stopped according to clinicians.

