**Statistical analysis data set**

- **Full analysis set (FAS):** All subjects who were enrolled and had at least one dose of investigation product along with efficacy evaluation were included in FAS as per the intention-to-treat (ITT) principles. FAS contributes to the main population for efficacy evaluation in this study.
- **Per-protocol set (PPS):** PPS includes all subjects who have fulfilled the protocol-required treatment or have not seriously violated the protocol. The exact definition of serious violation will be finalized during data review, which includes but not limited to the following conditions: fails to meet the main inclusion criteria, experiences the treatment that significantly interferes with efficacy evaluation after enrollment, poor compliance, poor follow-up record that significantly beyond the time window. PPS contributes to the secondary population for efficacy evaluation in this study. However, if the analysis results of PPS are inconsistent with the FAS, detailed analysis of the inconsistent results is required.

- **Safety set (SS):** SS is defined as the data that collected from subjects receiving at least one dose of investigation product.

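### Patients withdrawn for adherence, a prohibited medicine or a discontinuing adverse event before meeting the 7-day criterion have no defined primary outcome, and no platelet counts are planned after withdrawal.

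*Combined protocol and SAP*

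**What the plan says.** The Withdrawal criteria in the combined protocol and SAP include three events that occur after randomisation:

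- item 3, poor compliance: "medicine taken less than 80% of the prescribed amount", or above 120% of it;
- item 4: "With requirement of a medicine that is prohibited in the study";
- item 5: "With adverse events that discontinues the study".

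The list does not separate stopping study drug from leaving the trial. Item 1 gives the consequence as "receive other treatment after withdrawal from the study", and item 8 also refers to unsuitability for the study rather than for the drug.

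The primary outcome requires a platelet count of at least 20×10⁹/L "without the need for PLT transfusion for consecutive 7 days during core study". Treatment Design describes follow-up after study drug ends only for patients who achieved reconstruction. Concomitant Treatment item 7 calls for adverse events and concomitant medication to be observed in all participants until the end of the study. It does not mention platelet counts and does not say whether it applies after withdrawal.

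The full analysis set (FAS) invokes intention-to-treat but is limited to enrolled patients who "had at least one dose of investigation product along with efficacy evaluation". No rule is given for a missing primary outcome. Poor compliance is also listed as grounds for exclusion from the per-protocol set (PPS). The Sample size estimation adds an allowance: "Further taking into account a 20% shedding rate per group".

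**The concern.** Adherence, need for a prohibited medicine and discontinuing adverse events all arise after randomisation, and each may be related to response or to arm. One arm takes an oral tablet with food and the other receives a subcutaneous injection, so adherence may differ between them. The only prohibited medicines named are other thrombopoietin receptor agonists, so patients withdrawn under item 4 may tend to be those not responding.

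If platelet counts stop at withdrawal, the comparison rests on a selected subset. Calling the analysis intention-to-treat does not supply counts that were never taken. The analysis-set definitions also fit poorly with the withdrawal rule: excluding poor compliers from the PPS implies that they remain in the FAS, yet item 3 removes them from the study.

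**Working it through.** **Inputs.** From Sample size estimation: response 35% (control) and 60% (avatrombopag), two-sided α = 0.05, power 90%, 79 per arm, 20% shedding, 95 per arm. The loss rates used below are assumptions. The plan gives no rate for items 3–5, and its 20% covers loss from any cause.

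**The plan's own figure.** With unpooled variance, n = (1.960 + 1.282)² × (0.35×0.65 + 0.60×0.40) / 0.25² = 10.507 × 0.4675 / 0.0625 = 78.6, so 79 per arm, as stated. The plan's 95 is 79 × 1.2 = 94.8. Dividing by 0.8 would give 98.75, so 99.

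**What happens to a patient withdrawn in the core study.**

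| Situation at withdrawal | Primary outcome under the plan |
|---|---|
| 7-day criterion already met | Known: responder |
| Not met, some efficacy evaluation exists | In the FAS, classification undefined |
| Not met, no efficacy evaluation | Outside the FAS |

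**Extreme-case bounds.** Let L be the fraction lost per arm, with 0.60 and 0.35 observed among those retained.

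- Lower limit (every lost avatrombopag patient a non-responder, every lost control patient a responder): 0.60(1−L) − [0.35(1−L) + L].
- Upper limit (the reverse): [0.60(1−L) + L] − 0.35(1−L).
- L = 0.20: 0.48 − (0.28 + 0.20) = 0.00, to (0.48 + 0.20) − 0.28 = 0.40.
- L = 0.10: 0.54 − (0.315 + 0.10) = 0.125, to (0.54 + 0.10) − 0.315 = 0.325.

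**Power at 35% versus 60%** (pooled two-proportion test, 95 per arm):

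| Handling | Power |
|---|---|
| All followed to the end of the core study | 93.8% |
| 20% per arm lost at random and excluded (95 × 0.8 = 76 per arm) | 87.8% |
| 20% per arm counted as non-responders (0.60×0.8 = 48% versus 0.35×0.8 = 28%) | 81.6% |

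The plan also states a total of 78 participants. At 39 per arm the same three figures are 60.2%, 50.7% and 44.3%. The conflict between 78 and 190 is a separate matter to reconcile.

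**Bias as well as imprecision, in a deliberately one-sided case.** Suppose both true rates are 35%, there are 95 per arm, and only non-responders in one arm are withdrawn and excluded. With 10% of that arm removed, its observed rate becomes 0.35/0.90 = 38.9%; with 20% removed, 0.35/0.80 = 43.75%. The chance of a significant result in its favour is then about 7.8% or 21.4%, against a nominal 2.5%.

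**The case against.** Several stronger readings are tempting, and the documents do not support them.

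- **That any adverse event leads to withdrawal.** Item 5 covers only adverse events that lead to discontinuation.
- **That every withdrawn patient's outcome is lost.** A patient who already met the 7-day criterion has a known outcome. With visits roughly weekly from day 21, many others would have an efficacy evaluation and stay in the FAS. Loss is inferred from the absence of any provision for collection; the plan does not state it.
- **That item 3 must cost primary data.** No time for assessing adherence is given. If it is totalled only at the end of the core study, withdrawal on that ground would cost no primary data.
- **That nothing is recorded afterwards.** The visit schedule lists platelet transfusion under concomitant medication, so Concomitant Treatment item 7 may cover the transfusion half of the endpoint. It does not cover counts, and its reach after withdrawal is unclear.
- **That these rules lose 20% of patients, or that loss differs by arm.** The 20% is an allowance for all causes. The plan has no adherence or tolerability data by arm, so differential loss is a risk and not a finding. Both the bounds and the one-sided example rest on extreme assumptions.

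These points limit the size of the problem. They do not supply platelet counts after withdrawal or a rule for classifying the outcome.

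**Conclusion.** The point holds as a low-cost improvement to the plan. Items 3–5 can remove patients from the study after randomisation, and nothing in the document provides for their later platelet counts or says how their primary outcome is counted. A patient withdrawn before meeting the criterion in the core study has no defined primary outcome.

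The documents do not allow the actual size to be estimated. The ranges of 0 to 40 points at 20% loss and 12.5 to 32.5 points at 10% are limits under assumed all-cause loss with 60% and 35% observed. They are not forecasts, and they do not show that the result would be biased. They show that, at the plan's own allowance, the data alone could not exclude a zero difference among all randomised patients without an assumption about those missing. Counts not collected at the time cannot be recovered at analysis.

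**What to change.** No change is proposed to when treatment stops. The changes are to data collection and classification:

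1. State that, whatever is decided about study treatment, outcome collection continues. Record platelet counts and transfusions at visits 2–5 (days 21 to 42, already scheduled) for every randomised patient who has not withdrawn consent.
2. Analyse each such patient in the assigned arm in the FAS, and align the FAS wording and item 3 with this.
3. Pre-specify how the primary outcome is classified after each of these events, including whether a response that follows a prohibited medicine counts.
4. Count patients with no usable data as non-responders, and report best- and worst-case bounds as a sensitivity analysis.

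The cost is protocol wording and a few visits kept for more patients. Some power is lost where outcomes are still missing: if 20% per arm were counted as non-responders at 95 per arm, power would be about 82%, against about 94% with complete follow-up. Continued collection keeps that number small.
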